5.5.6 Rescue medication

Not applicable.

5.5.7 **Concomitant Treatment**

The investigator should instruct the subject to notify the study site about any new medications he/she takes after the subject was enrolled into the study. All medications, procedures and significant non-drug therapies (including physical therapy and blood transfusions) administered after the subject was enrolled into the study will be recorded on the Concomitant Medications CRF or the Surgical and Medical Procedures CRF respectively.

CMV prophylaxis

Cytomegalovirus (CMV) pre-emptive therapy and/or prophylaxis is recommended for all donor CMV positive/recipient CMV negative cases and considered for all recipients who are CMV positive. It is recommended that CMV prophylaxis be administered for a minimum of three months after transplantation. Prophylactic treatment with i.v. ganciclovir or oral valgan ciclovir is recommended and will be administered according to local practice, taking into account dose adjustments based on renal function. CMV prophylaxis is also recommended following antibody treatment of acute rejection episodes (see Section 5.5.5 above). Such prophylaxis should be recorded on the Concomitant Medications CRF.

Pneumocystis jirovecii (Pneumocystis carinii) pneumonia prophylaxis

All subjects will be started on trimethoprim-sulfamethoxazole, starting when oral medication can be tolerated and continuing until at least six months post-transplant. After six months, subjects will be treated per local practice. Aerosolized pentamidine or dapsone may be administered to subjects who are unable to tolerate trimethoprim-sulfamethoxazole.

These prophylactic treatments above must be applied consistently across the study population at each given center to avoid bias and confounding in the results. Such prophylaxis should be recorded on the Concomitant Medications CRF.

Treatment of hyperlipidemia

During the course of the study, the lipid profile will be monitored. Lipid lowering medications should be administered according to guidelines and local practice.

The combination of HMG-CoA reductase inhibitors concomitantly with fibrates should be avoided, due to the increased risk of myopathy and rhabdomyolysis in combination with cyclosporine. If combination therapy is needed, ezetimibe should be used in combination with statins. Lipid lowering therapy should be optimized before dosage reduction of study medication is considered.

Hepatitis B (HBV) prophylaxis

Prophylaxis for recurrent hepatitis B during the course of this study is allowed and will be administered at the discretion of the investigator.

Prohibited Treatment 5.5.8

Use of the treatments displayed in Table 5-3 is NOT allowed after informed consent up to the end of the 24 Month treatment period. If the use of any of these medications or other nonprotocol immunosuppressives is discovered prior to randomization subject must not be randomized and recorded as a screen failure. If discovered after randomization no further doses are to be given and the subject should continue on the randomized treatment regimen, noting the protocol deviation.

Table 5-3 Prohibited medications

Medication	Action to be taken
Advagraf®	Discontinue Advagraf®, Subject to remain in study with protocol deviation.
Sirolimus	Discontinue sirolimus, Subject to remain in study with protocol deviation.
Belatacept	Discontinue belatacept, Subject to remain in study with protocol deviation.
Azathioprine	Discontinue azathioprine, Subject to remain in study with protocol deviation.
Induction therapy with Campath or other non-protocol antibody agents	Agent to be discontinued and subject to remain in study with protocol deviation.

5.5.9 Discontinuation of study treatment and discontinuation from study

Discontinuation of study regimen

The Dosage administration records for everolimus, MPA, tacrolimus and cyclosporine will be used to record if a subject has permanently discontinued study treatment and why.

Possible reasons for study treatment discontinuation are:

- Adverse Event
- Lack of Efficacy
- Technical problems
- Subject/Guardian Decision
- Lost to follow-up
- Death
- Graft Loss

The investigator should discontinue a subject from their randomized treatment regimen if, on balance, he/she believes that continuation would be detrimental to the subject's well-being.

If, at any time throughout the study, the randomized treatment regimen or any component of the regimen is interrupted for longer than 21 consecutive days, unless being held due to an elective surgical procedure then study regimen should be discontinued.

Subjects who become pregnant while taking study medication must be discontinued from study medication and from the study, such pregnancies should be reported as SAEs to Novartis DSE and entered as AEs in the CRF, the reason for discontinuation of study medication should be recorded as AE and reason for discontinuation from study is pregnancy (see next section below).

Subjects who discontinue their randomized study regimen (any component whether everolimus, MPA or the CNI) should remain in the study, if possible, and receive standard of care immunosuppression, according to local practice, until completing the study at Month 24. Visits and assessments for such subjects are described in Table 6-1. All immunosuppressants after

discontinuation of study regimen must be recorded on the Concomitant Medication CRF under the Immunosuppressive category.

Subjects are expected to remain on the original CNI (combined with everolimus or MPA) to which they were randomized until at least Month 24. However, if subjects discontinue either CNI due to AE/tolerability and maintain everolimus or MPA combined with the alternate CNI, administered to respective target levels per protocol, they will not be considered to have discontinued study regimen/medication.

Discontinuation from Study and Study/Period completion

Subjects who discontinue their study treatment regimen should NOT be considered withdrawn from the study. Such subjects should remain in the study, if possible, and receive standard of care immunosuppression, according to local practice, until completing the study at Month 24. See Table 6-1 for the required assessments of these subjects after discontinuation of study regimen.

The status of every randomized subject must be recorded on Month 12 and/or Month 24 Study Phase Completion CRFs as either completing or discontinuing from the respective study period, with reason for discontinuation.

Possible reasons for discontinuation from the study are:

- Technical problems
- Subject/Guardian Decision
- Lost to follow-up
- Death
- **Graft Loss**
- Study terminated by sponsor
- Pregnancy

Subjects may voluntarily withdraw from the study for any reason at any time. They may be considered withdrawn if they state an intention to withdraw, fail to return for visits, or become lost to follow-up for any other reason.

If premature withdrawal occurs for any reason, the investigator must make every effort to determine the primary reason for a subject's premature withdrawal from the study and record this information on the Study Phase Completion CRF at Month 12 and/or Month 24 as applicable.

For subjects who are lost to follow-up (i.e. those subjects whose status is unclear because they fail to appear for study visits without stating an intention to withdraw), the investigator must show "due diligence" by documenting in the source documents steps taken to contact the subject, e.g. dates of telephone calls, registered letters, etc.

Subjects who are prematurely withdrawn from the study will not be replaced.

5.5.10 **Emergency breaking of treatment assignment**

Not applicable.

Study completion and post-study treatment 5.5.11

Subject who successfully complete 24 months on treatment may be eligible to participate in a separate observational extension study for a further three years. Subjects who are prematurely withdrawn from the study should be treated according to local standard of c are per investigator's judgment.

The study will be complete and ready for final analysis when the last active subject has completed their Month 24 visit.

5.5.12 Early study termination

The study can be terminated at any time for any reason by Novartis. Should this be necessary, the subject should be seen as soon as possible and treated as for a prematurely withdrawn subject. The investigator may be informed of additional procedures to be followed in order to ensure that adequate consideration is given to the protection of the subject's interests. The investigator will be responsible for informing IRBs and/or ECs of the early termination of the trial.

6 Visit schedule and assessments

Table 6-1 lists all of the assessments and indicates with an "X" when the visits are to be performed. "A" indicates assessments only to be performed for subjects maintaining the study regimen (i.e. EVR+CNI or MPA+CNI). Subjects should be seen for all visits on the designated day or as close to it as possible.

The day of randomization will be considered to be study Day 1. Subjects will make scheduled study visits on Day 4, at the end of Weeks 1, 2 and 4 at the end of Months 2, 4, 6, 9, 12, 18 and 24. All randomized subjects are expected to continue in the study up to Month 24 regardless of being on or off randomized treatment status. Subjects who discontinue their randomized study treatment regimen should be treated according to standard of care immunosuppression and return for the assessments indicated by X in Table 6-1. If they refuse to return for these assessments or are unable to do so, every effort should be made to contact them or a knowledgeable informant by telephone to determine the subject and graft status.

At a minimum, subjects will be contacted for safety evaluations (SAEs) during the 30 days following the last study visit. Documentation of attempts to contact the subject should be recorded in the source documentation.

Assessment schedule- Study Treatment to Month 24 Table 6-1

Study Period	Screening ¹		Treatment to Month 12									Extension Treatment to Month 24		
Visit	SCR	BL ²	D4	W1	W2	W4	M2	M4	М6	М9	M12	M18	M2 4	
Visit Number	1	99	101	102	103	104	105	106	107	108	199	201	299	
Informed Consent ¹	Х													
Demographics	Х													
Inclusion/	X	Х												
Exclusion														
Medical History	Х												 	
Kidney Transplant Background Recipient/Donor		X												
Kidney Transplant Procedure		Х												
Viral serology ³ Recipient/Donor		Х												
Pregnancy test ⁴	Х								Х		Х	Х	Х	
IRT call	S	S												
Screening Disposition ¹		Х												
Vital signs	Х	Х	Α	Α	Α	Α	Α	Α	Χ	Χ	Х	Х	Χ	
Physical exam	S										S		S	
Tacrolimus dose administration record ⁵			X	A	A	A	A	A	А	A	Α	Α	A	
Tacrolimus trough level ⁶				Х	Х	Х	Х	Х	Х	Х	Х	Х	Х	
Cyclosporine dose administration record ⁵			X	A	A	A	A	A	A	A	A	A	A	
Cyclosporine trough level ⁶				Х	Х	Х	Х	Х	Х	Х	Х	Х	Х	
Everolimus dose administration record ⁵			X	A	Α	Α	Α	Α	А	A	A	A	А	
Everolimus trough level ⁶				Α	Α	Α	Α	Α	Α	Α	Α	Α	Α	
MPA Dose administration record⁵			X	A	Α	Α	Α	Α	Α	A	Α	Α	Α	
Central Laboratory ⁷		Х		Α	Α	Α	Α	Α	Х	Х	Х	Х	Х	
Concomitant medication ⁸	As Needed													
Surgical and Medical Procedures	As Nee	As Needed												
Adverse events ⁹	As Needed													
CMV assessment	As Needed													
BKV assessment		As Needed												
Hospitalizations			As Ne											
Allograft rejection			As Nee	ded										

Amended Protocol Version v01 Clean

Study Period	Scree	ning¹	Treatr	ment to	Month	12						Extens Treatn to Moi	nent
Visit	SCR	BL ²	D4	W1	W2	W4	M2	M4	М6	М9	M12	M18	M2 4
Visit Number	1	99	101	102	103	104	105	106	107	108	199	201	299
Kidney allograft biopsy			As Nee	ded									
Graft loss			As Ne	eded									
Dialysis log			As Ne	eded									
Death	As Ne	eded											
Withdrawal of Informed Consent	As Ne	eded											
Month 12 Period Completion ¹⁰			As Ne	eded							Х		
Month 24 Period Completion ¹⁰											As nee	eded	Х

X=assessment for all subjects in study regardless of on or off randomized study regimen, to be recorded in clinical data base A=assessment ONLY for subjects maintaining their randomized study regimen, to be recorded on clinical data base S=assessment to be recorded on source documentation

- 1. Informed consent should be obtained prior to performing any study-related procedures. Screening may extend up to 4 weeks prior to transplant e.g. for scheduled living donor transplants and ends when the subject is either randomized or becomes a screen failure. For every consented subject the Screening period disposition CRF must be completed to indicate whether they were randomized or screening failures.
- 2. The Baseline visit covers the transplant period from 24 hr prior to surgery until randomization or randomization failure. Randomization must occur within 24 hr of completion of transplant surgery and post-transplant criteria for randomization (e.g. ability to take oral medication) must be met. Day 1 is the day of first dose of study drug post-randomization and for subsequent visits one week is 7 days and one month is 30 days, thus the Week 1 visit is on the seventh day from Day 1.
- 3. Viral serology includes HCV, HIV, HBV surface antigen, CMV and EBV. Measurements made within the last 6 months will be accepted, otherwise these tests should be performed within one week of randomization.
- 4. Only for females of child bearing potential, serum pregnancy tests should be carried out according to local practice. Local result must be available and negative prior to randomization.
- 5. First dose of everolimus or MPA together with applicable CNI (tacrolimus or cyclosporine) must be given immediately following randomization and within 24 hr of transplantation. Pre-transplant immunosuppression, including induction therapy and any CNI or MPA should be recorded on the Concomitant medication CRF under the immunosuppressive category.
- 6. Blood draws for everolimus, tacrolimus and cyclosporine (as applicable) trough concentrations should be performed locally as shown and additionally 5 days ± 2 days following each clinic visit in which tacrolimus, cyclosporine or everolimus doses are changed. Subject clinical management should be based on these local trough levels. At certain centers, by agreement with the sponsor, central analysis of everolimus may be performed.
- 7. Central laboratory tests at each visit indicated include: **Biochemistry** (sodium, potassium, chloride, calcium, Cystatin C, magnesium, inorganic phosphate, urea, creatinine, uric acid, AST, ALT, alkaline phosphatase, total bilirubin, CPK, lipase and amylase); Hematology (platelets, hemoglobin, red blood cell (RBC), white blood cell (WBC) and differential count): Lipids: total cholesterol, HDL, LDL and triglycerides Urinalysis (protein, creatinine, albumin, glucose; proteinuria and albuminuria per 24hr period will be estimated from spot protein/creatinine and albumin/creatinine ratios). For subjects who have discontinued study regimen who continue in the study to Month 24 all central laboratory assessments, including serum creatinine for renal function, should be performed, where no central laboratory serum creatinine is available local laboratory serum creatinine should be obtained. HbA1c and fasting plasma glucose will also be carried out by the central laboratory at Week 4 and Months 4, 6, 9, 12 18 and 24. At certain centers, in agreement with the sponsor, central analysis of everolimus levels may be performed.
- 8. Induction therapy (basiliximab or rATG) should be recorded on the Concomitant Medications CRF under the Immunosuppressive Medications category. Pre-transplant CNI or MPA, if used, should be also recorded on the Concomitant medication CRF under the immunosuppressive category.
- All serious adverse events, serious infections and pregnancies must be reported from informed consent until 30 days after the last study visit post randomization (i.e. to the Month 12/24 visit or early discontinuation from study).
- 10. All subjects are expected to continue in the study to Month 24 regardless of whether they are on or off randomized study regimen, if subjects discontinue randomized study regimen they should continue on standard of care and attend study visits to M24. Any permanent discontinuation of the randomized study regimen should be recorded on the appropriate DAR(s) (everolimus MPA, tacrolimus or cyclosporine as needed). Post discontinuation of study regimen the immunosuppressive

Amended Protocol Version v01 Clean

Study Period	Screen	ning¹	Treatm	ent to	Month	12						Extens Treatn to Mor	nent
Visit	SCR	BL ²	D4	W1	W2	W4	M2	M4	М6	М9	M12	M18	M2 4
Visit Number	1	99	101	102	103	104	105	106	107	108	199	201	299

regimen prescribed should be recorded on the Concomitant medication CRF under the immunosuppressive category and any CNI trough levels should be recorded on the appropriate local lab trough CRF.

For subjects who have discontinued randomized study regimen, visits need only be completed at Months 6, 9, 12, 18 and 24. For all subjects completing the study to Month 12 or discontinuing from the study prior to Month 12, the M12 Period completion form should be completed, regardless of on or off-treatment status. Similarly post-Month 12, for all subjects completing the study to Month 24 or discontinuing from the study prior to Month 24, the M24 Period completion form should be completed, regardless of on or off-treatment status.

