2.2 Secondary objectives

Key Secondary Objectives

- To evaluate everolimus with reduced exposure CNI compared to MPA plus standard exposure CNI at 12 months post-transplantation with respect to the composite efficacy failure rate of (treated biopsy proven acute rejection (tBPAR), graft loss or death).
- To evaluate the binary composite endpoint of tBPAR or eGFR < 50 mL/min/1.73m² (MDRD4) Month 12 among compliant subjects.

Other Secondary Objectives

To evaluate, by treatment group;

- The incidence of composite endpoint of tBPAR or eGFR < 50 mL/min/1.73m² (MDRD4) at Month 24.
- The incidence of composite endpoint of tBPAR (excluding Banff grade 1A acute rejections) or eGFR < 50 mL/min/1.73m² (MDRD4) at Month 24.
- The incidence of composite endpoint of tBPAR or eGFR < 50 mL/min/1.73m² (MDRD4) at Month 12 by subgroup (see Section 9.4.4).

- The incidence of composite endpoint of tBPAR, graft loss or death at Month 24.
- The incidence of composite endpoint of tBPAR, graft loss, death, or loss to follow-up at Months 12 and 24.
- The incidence of composite endpoint of tBPAR, graft loss, death or eGFR < 50 mL/min/1.73m² at Months 12 and 24.
- The incidence of composite endpoint of graft loss or death at Month 12 and 24.
- The incidence of individual endpoints of death, graft loss, tBPAR, BPAR, tAR, AR and humoral rejection at Months 12 and 24.
- The incidence of tBPAR by severity and time to event.
- The incidence of tBPAR excluding Banff 1A grade acute rejections
- The incidence of transplant recipients with eGFR < 50 mL/min/1.73m² at Months 12 and 24.
- Renal allograft function and change in renal allograft function from Month 1 (eGFR) at Months 12 and 24.
- The evolution of renal function, as eGFR, over time by slope analysis.
- Renal function by Cystatin C-based and other alternate formulae (e.g. CKD-EPI).
- The incidence of adverse events, serious adverse events and adverse events leading to study regimen discontinuation.
- The incidence of CMV and BKV, new onset diabetes mellitus, chronic kidney disease with associated proteinuria and CNI associated adverse events.
- Urinary protein and albumin excretion by treatment estimated by urinary protein/creatinine and urinary albumin/creatinine ratios.
- The incidence of major cardiovascular events.
- The incidence of malignancies.

3 Investigational plan

[figure not shown]

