8.3 Database management and quality control

Novartis staff will review the data entered into the CRFs by investigational staff for completeness and accuracy and instruct the site personnel to make any required corrections or additions. Queries are sent to the investigational site using an electronic data query. Designated investigator site staff are required to respond to the query and confirm or correct the data.

Concomitant medications entered into the database will be coded using the WHO Drug Reference List, which employs the Anatomical Therapeutic Chemical classification system. Concomitant procedures, non-drug therapies and adverse events will be coded using the Medical dictionary for regulatory activities (MedDRA) terminology.

Laboratory samples will be processed centrally and the results will be sent electronically to Novartis.

Randomization codes will be assigned using Interactive Response Technology (IRT). The IRT system will be supplied by a vendor, who will also manage the database. The database will be sent electronically to Novartis.

Protocol deviations will be identified, documented and communicated as required throughout the study. At the conclusion of the study, the occurrence of relevant protocol deviations will be determined. After these actions have been completed and the database has been declared to be complete and accurate, it will be locked and the treatment codes will be unblinded and made available for data analysis. Any changes to the database after that time can only be made after written agreement by Novartis Development management.

Amended Protocol Version v01 Clean

Not applicable.

8.4

8.5 **Adjudication Committee**

Data Monitoring Committee

Not applicable.

9 Data analysis

Statistical analysis and report writing will be performed when the last subject has completed 12 months on study. A second and final analysis will be performed when all subjects complete 24 months of the study.

9.1 **Analysis sets**

The full analysis set (FAS) consists of all randomized and transplanted subjects. Subjects randomized but not transplanted will be excluded from the FAS. Subjects who are misrandomized due to documented (IVRS) administrative error (eligibility criteria) and have no study drug received are excluded from the FAS. Following the intention-to-treat (ITT) principle, subjects will be analyzed according to their randomized treatment assignment and according to the actual stratum they belong to.

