9.5.2 Other secondary efficacy variables

Other secondary efficacy variables to be considered are as follows:

- (1) Composite endpoint of tBPAR or eGFR (MDRD4) < 50 mL/min/1.73m² at Month 24;
- (2) Composite endpoint of tBPAR excluding grade IA rejections or eGFR (MDRD4) < 50 mL/min/1.73m² at Months 12 and 24
- (3) Composite efficacy failure of tBPAR, graft loss, or death at Month 24;
- (4) Composite efficacy failure of tBPAR, graft loss, death, or loss to follow-up at Month 12 and 24;
- (5) Components of composite efficacy failure as well as BPAR, AR, tAR at Month 12 and Month 24;
 - a) AR
 - b) tAR
 - c) BPAR;
 - d) tBPAR;
 - e) tBPAR excluding grade IA rejections;
 - f) Humoral rejection
 - g) Graft loss;
 - h) Death.
- (6) composite endpoint of tBPAR, graft loss, death or eGFR < 50 mL/min/1.73m² at Months 12 and 24;
- (7) Composite endpoint of graft loss or death at Month 12 and Month 24;
- (8) Composite endpoint of BPAR, graft loss or death at Month 12 and Month 24;
- (9) eGFR (MDRD4) $< 50 \text{ mL/min}/1.73\text{m}^2$ at Month 12 and Month 24;
- (10) Renal function (eGFR by MDRD4, CKD-EPI and Cystatin C-based formulae) at Month 12 and Month 24;
- (11) Renal function change from Month 1 (Week 4) to Month 12 and Month 24;
- (12) Evolution of renal function (eGFR by MDRD4) from Month 1 to Month 12 and Month 24 (slope analyses).

The analyses on efficacy endpoints and renal function will be based on the Full Analysis Set. Selected parameters will be analyzed on the Per-Protocol Set as well.

A Z-test based comparison will be performed for the following composite endpoints: tBPAR or eGFR (MDRD4) < 50 mL/min/1.73m² at Month 24, composite endpoint of tBPAR excluding grade IA rejections or eGFR (MDRD4) < 50 mL/min/1.73m² at Months 12 and 24, endpoint of tBPAR, graft loss, death or eGFR < 50 mL/min/1.73m² at Months 12 and 24, and endpoint of tBPAR, graft loss, death, or loss to follow-up at Months 12 and 24.

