### 2.7.3.2 eGFR by MDRD4

The eGFR by MDRD4 analyses will be based on FAS with multiple imputation used as the primary method for the handling of missing data. Renal function and change from Week 4 will be summarized by visit with descriptive statistics. A two-sided t-test will be performed to compare the two treatment groups at each visit. A plot of mean and 95% CI of eGFR (MDRD4) by visit will be provided. These will be repeated for on-treatment renal function analyses.

In addition, if different CNI effect is shown from the logistic regression, eGFR(MDRD4) and change in eGFR(MDRD4) from Week 4 by visit will be summarized for the subgroups of CNI (CsA and TAC).

The proportion of patients by eGFR(MDRD4) range (<30, 30-<45, 45-<60, ≥60 mL/min/1.73m^2) will be summarized by visit.

For eGFR(MDRD4) at Month 12 and Month 24, analysis of covariance (ANCOVA) will be performed with covariates/factors of treatment, CNI, region, interaction of treatment and CNI, interaction of treatment and region, donor type, HLA mismatch (≤3 vs >3), induction therapy, recipient gender, recipient age, donor age, DGF, and eGFR (MDRD4) at Month 1. In the model, recipient and donor age will be treated as continuous variables. The missing Month 12 or Month 24 values will be imputed using the primary multiple imputation method.

The evolution of renal function (eGFR by MDRD4) will be evaluated via a mixed effect model with intercept and study day as random effects and using covariates/factors treatment, study day, CNI, region, interaction of treatment and study day, interaction of treatment and CNI, interaction of treatment and region, donor type, HLA mismatch (≤3 vs >3), induction therapy, recipient gender, recipient age, donor age, DGF, and eGFR (MDRD4) at Month 1. In the model, study day, recipient and donor age, and eGFR (MDRD4) at Week 4 will be treated as continuous variables. Unstructured variance-covariance can be assumed, and the eGFR (MDRD4) data at Week 4 and onward will be used. The denominator degrees of freedom will be calculated using the Kenward-Roger method. No imputation will be applied for missing data. Based on the mixed effect model, the treatment groups will be compared, slope of renal function evolution for each treatment group will be assessed, and eGFR(MDRD4) value at Month 12/24 will be estimated.

See dummy SAS codes below.

```
proc mixed method=ml;
  class trt CNI region donor HLA induction gender_r DGF usubjid;
```

```

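### The eGFR slope model and the treatment-by-CNI interaction test drop patients who stop the regimen before Week 4, because both need a Week 4 eGFR that is neither required from these patients nor imputed

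*Protocol*

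**What the plan says.** **Objectives and population.** Protocol Section 2.2 lists, by treatment group, "change in renal allograft function from Month 1 (eGFR) at Months 12 and 24" and "The evolution of renal function, as eGFR, over time by slope analysis". Section 9.5.2 adds: "The analyses on efficacy endpoints and renal function will be based on the Full Analysis Set". Section 9.1 defines that set: "The full analysis set (FAS) consists of all randomized and transplanted subjects".

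**What is collected.** In Table 6-1 the central laboratory row carries the code A at Weeks 1, 2 and 4 and Months 2 and 4, and the code X (all subjects) from Month 6. The key reads "A=assessment ONLY for subjects maintaining their randomized study regimen". The text closing footnote 10 says: "For subjects who have discontinued randomized study regimen, visits need only be completed at Months 6, 9, 12, 18 and 24". Footnote 7 points the other way. For discontinuers who stay in the study, it says "all central laboratory assessments, including serum creatinine for renal function, should be performed", with local creatinine as back-up, but it names no visits. CNI troughs are coded X at the same early visits.

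**What the analyses need.** SAP 2.7.3.2 fits a mixed model to eGFR (MDRD4) from Week 4 onward. Month 1 eGFR is among the covariates (eGFR_1 in the sample code), and the rule is "No imputation will be applied for missing data". The treatment-by-CNI interaction model in SAP 2.5.2 is run on the full analysis set without imputation and also contains Month 1 eGFR. In contrast, SAP 2.7.3.2 analyses MDRD4 eGFR and its change from Week 4 with multiple imputation, and the sample code in SAP 4.2.1.1 lists the eGFR of every visit.

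**The concern.** The protocol means to follow every randomised patient to Month 24, on or off the regimen. A patient who stops in the second week and returns from Month 6 supplies several eGFR values, yet a model that requires an unimputed Week 4 value discards all of them. The exclusion is caused by an event after randomisation. That event can differ in frequency and in reason between the arms, and it may single out patients with early toxicity.

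Two results are exposed. One is the slope comparison, with the Month 12 and 24 eGFR read from the same model. The other is the interaction test. If that test is significant at 0.10, the CNIs are tested separately and the tacrolimus subgroup becomes primary.

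**Working it through.** The plan states no figure to reproduce here, so the check traces the rules and then sizes the consequence.

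**1. Who is affected.** All of the following must hold:
- The patient permanently stops before the Week 4 visit. Anyone stopping later keeps a Week 4 value.
- The patient stays in the study and gives eGFR from Month 6.
- No creatinine is reported in the Week 4 window, Days 22 to 44 (SAP Table 4-1). SAP 4.1 re-aligns reported unscheduled values into windows, so a stray value would rescue the patient.

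**2. What each analysis does with such a patient.**

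| Analysis | Needs Week 4 eGFR | Missing-data rule | Result |
|---|---|---|---|
| Slope model (SAP 2.7.3.2) | Covariate | None | All records dropped |
| Treatment-by-CNI interaction (SAP 2.5.2) | Covariate | None | Patient dropped |
| MDRD4 change from Week 4 (SAP 2.7.3.2) | Reference value | Multiple imputation | Kept, on an imputed reference |
| ANCOVA at Month 12/24 (SAP 2.7.3.2) | Covariate | Stated for Month 12/24 values only | Unclear |
| CKD-EPI and cystatin C (SAP 2.7.3.1) | Reference value | On-treatment, no imputation | On-treatment by design |

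**3. Mechanical check of the slope model.** In a constructed data set of 400 subjects, 18 had no Month 1 eGFR but did have Month 6, 9 and 12 values. Fitting with the Month 1 covariate and no imputation left 400 − 18 = 382 subjects, so all 18 were lost.

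**4. Number lost per arm.** Patients lost = 1020 × d, where d is the share meeting the conditions in step 1. The documents do not give d, so a range is assumed:
- d = 1%: 10
- d = 2%: 20
- d = 5%: 51
- d = 10%: 102

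Cyclosporine is capped at 20% of the population, or 0.20 × 1020 = 204 per arm. In that stratum the same shares mean about 2 to 20 patients.

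**5. Illustrative bias.** Let dE and dM be the shares lost in the everolimus and MPA arms. Let D be the mean outcome of those lost minus that of the rest, taken as equal in both arms. An arm's full mean is its retained mean plus d × D. The retained-patient difference (EVR minus MPA) is therefore off by −(dE − dM) × D. With assumed values, in mL/min/1.73m²:
- 2% against 2%, any D: 0
- 5% against 2%: −0.03 × −5 = 0.15; at D = −10, 0.3; at D = −20, 0.6
- 10% against 5%: −0.05 × −5 = 0.25; at D = −10, 0.5; at D = −20, 1.0

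A positive value flatters the arm with more early stopping. The formula is for an unadjusted mean level and gives no bias for the slope itself. Because the model adjusts for DGF, donor type, donor age, HLA mismatch and other factors, D is best read as what remains after that adjustment.

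**The case against.** The best defence is that few patients are exposed and part of the gap is already covered. Footnote 7 can be read as asking for creatinine at every visit. If a CNI trough is drawn at Week 4, a local creatinine probably exists. An interruption ends the regimen only after more than 21 consecutive days, so a patient who pauses in the second week is not necessarily off the regimen at Day 28. Some patients with early graft problems leave the study (graft loss, or the DGF rule in Protocol 5.5.5) and have no later eGFR to recover. The slope is item 12 of the other secondary endpoints and lies outside the testing hierarchy. Month 12 and 24 eGFR is also compared on multiply imputed full-analysis-set data.

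Most of this stands, and it limits the size of the problem. It does not remove it. Footnote 7 names no visits and conflicts with the A code and with footnote 10. Unscheduled values are usable but not required. The slope model as written still discards the collected follow-up of anyone who falls in the gap. Nor is the interaction test a minor endpoint, since it decides which population is primary.

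A reader might also infer that early discontinuers fall out of the change-from-Month-1 comparison. The documents do not support that for MDRD4. The analysis is on the full analysis set with multiple imputation, and the sample code covers the visit eGFRs. The weakness there is milder: the Week 4 reference is imputed under MAR, largely from patients who stayed on the regimen. The SAP prose speaks of imputing the 12-month value, so filling Week 4 is visible only in the code.

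**Conclusion.** The point holds for the slope model, for the Month 12 and 24 eGFR estimated from it, and for the treatment-by-CNI interaction test. In each, a full-analysis-set patient can be excluded for lacking a value the schedule did not require. For the ANCOVA the handling is unstated. The imputed primary composite does not itself need a Week 4 value; it is touched only through the pooling decision.

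The size is uncertain and probably modest. At assumed shares of 1% to 10%, about 10 to 102 of 1020 per arm are lost. On the formula above, the bias in mean level is zero if the shares are equal or if those lost do no worse than the rest, and 0.15 to 1.0 mL/min/1.73m² in the unequal scenarios tried. The shares and outcome deficits are assumptions, not figures from the documents. The effect on the interaction test has not been quantified. The correction is still worth making, because it is cheap and restores the stated analysis population.

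**What to change.** **SAP.**
- Fit the slope and interaction models with the Week 4 covariate taken from the 100 imputed datasets of SAP 4.2.1.1, and combine by Rubin's rules. In the slope model, leave the outcome records as observed. No full-analysis-set patient with later eGFR is then excluded for a missing Week 4 value.
- State the same rule for the ANCOVA covariate, and say in the prose that Week 4 is imputed.
- SAP 4.2.1.1 assigns zero after graft loss, so say how a graft lost before Week 4 enters the interaction model.
- Last Patient First Treatment was 26 January 2016, so Month 12 (360 days) fell in January 2017, before the SAP version of 27 February 2018. If the interaction test has already been run, report the refit as a sensitivity analysis.

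**Protocol and data.**
- Reconcile the A code in Table 6-1, footnote 7 and footnote 10 on creatinine in off-regimen patients before Month 6.
- Because first treatment was complete by January 2016, changing the schedule can recover few if any Week 4 visits. The practical step is to enter local Week 4 creatinine for early discontinuers where it already exists, a source footnote 7 accepts.

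**Cost.** Some extra analysis work, chart retrieval for the early discontinuers, and an amendment under Protocol 11.1 if the schedule text is changed. The downsides are some mixing of local and central creatinine, and reliance on MAR for the Week 4 values that remain missing.
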